5.3.2. Medical and therapeutic criteria

15. Adequate haematological function based on the last assessment performed within 7 days prior to the first IMP administration, defined as:
 - Circulating white blood cell count < 10 G/L (only use of hydroxycarbamide or leukapheresis before study drug initiation is allowed to achieve this inclusion criterion)
16. a. Adequate renal function based on the last assessment performed within 7 days prior to the first IMP administration defined as calculated creatinine clearance > 60 mL/min/1.73m², determined by MDRD ([Appendix 4](#))
17. Adequate hepatic function based on the last assessment performed within 7 days prior to the first IMP administration defined as:
 - AST and ALT < 1.5 x ULN and
 - Total serum bilirubin level < 1.5 x ULN, except for patients with known Gilbert's syndrome (confirmed by the UGT1A1 polymorphism analysis) who are excluded if total bilirubin > 3.0 x ULN or direct bilirubin > 1.5 x ULN

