6.1.2. Administration/re-administration criteria

- Criteria to fulfil before each S64315 infusion
 - Before each S64315 infusion, biological parameters should be checked in order to detect any toxicity (see [Table \(8.12\) 1](#))
 - Patients with Grade ≥ 2 hypo/hypercalcemia and/or hypo/hypermagnesia and/or hypo/hyperkalaemia despite attempts at medical correction should not be treated with S64315
 - Patients with WBC ≥ 10 G/L despite attempts at medical correction should not be treated with S64315. Hydroxycarbamide can be used to reduce the circulating blast count before and throughout the treatment period
 - AST and ALT ≤ 3 x ULN (except for LID1: AST and ALT ≤ 1.5 x ULN)
 - Total bilirubin level ≤ 1.5 x ULN, except for patients with known Gilbert's syndrome, who are excluded if total bilirubin > 3.0 x ULN or direct bilirubin > 1.5 x ULN
 - In the case of an S64315 interruption ≥ 28 days, its readministration must be preceded by a lead-in dose period (except for patients in CR/CRi) which is called additional Lead-In dose period. See [Table \(4.1.2\) 1](#) for more details on safety assessments required.
- Criteria to fulfil before each first azacitidine administration (i.e. CxD1)

Patients should be monitored for haematological toxicity and renal toxicities. A delay in starting the next cycle or a dose adjustment due to haematological toxicity and/or renal toxicity may be necessary according to E.U. SmPC (see [Table \(8.12\) 2](#)). WBC, absolute neutrophil count (ANC), platelets, serum creatinine, BUN and serum bicarbonate will be assessed before starting the next treatment cycle.

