8.12. Management of treatment dose adaptations due to toxicities

For patients who do not tolerate the protocol-specified dosing schedule, dose interruptions and/or reductions are either recommended or mandated in order to allow patients to continue the study treatments.

Dose modifications recommendations for S64315 are summarised in [Table \(8.12\) 1](#).

A patient must discontinue treatment with S64315 if, after treatment is resumed at a lower dose, the toxicity recurs with the same or worse severity, unless in the opinion of the investigator it is in the patient's best interest to continue S64315, and upon documented agreement with the Sponsor.

For each patient, once a dose reduction has occurred, the dose may not be re-escalated during the subsequent cycles unless in the opinion of the investigator it is in the patient's best interest to continue S64315, and upon documented agreement with the Sponsor.

When a patient meets the criteria for S64315 discontinuation described in the table, he/she must discontinue both IMPs.

Dose modifications for azacitidine must be done according to azacitidine E.U. SmPC (see [Table \(8.12\) 2](#)).

These dose changes must be recorded in the eCRF.

Table (8.12) 1 - Criteria for interruption and re-initiation of S64315

Recommended dose modifications for S64315	
Worst toxicity CTCAE Grade^a (unless otherwise specified)	During a cycle of therapy
Investigations (Renal)	
Serum creatinine	
Grade 2 (> 1.5 – 3 x ULN or > 1.5 – 3 x baseline)	Omit dose until resolved to Grade ≤ 1 or baseline, then: - If resolved in ≤ 14 days, then maintain dose level - If resolved in > 14 days, then ↓ 1 dose level
Grade 3 (> 3 – 6 x ULN or > 3 x baseline)	Omit dose until resolved to Grade ≤ 1 or baseline, then ↓ 1 dose level
Grade 4 (> 6 x ULN)	Discontinue patient from test drug treatment
Note: If intercurrent illness, e.g. dehydration due to diarrhoea or febrile infections, leads to prerenal insufficiency, this should not be considered drug related and the criterion for dose modification not fulfilled	
Investigations (Hepatic)	
Isolated Total Bilirubin elevation^b	
Grade 2 (> 1.5 - 3.0 x ULN if baseline was normal, >1.5 - 3.0 x baseline if baseline was abnormal)*	Omit dose until resolved to Grade ≤ 1, then: - If resolved in ≤ 14 days, maintain dose - If resolved in > 14 days, ↓ 1 dose level

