Grade 3 (> 3.0 - 10.0 x ULN)	Omit dose until resolved to Grade ≤ 1, then: - If resolved in ≤ 14 days, ↓ 1 dose level - If resolved in > 14 days, discontinue patient from test drug treatment The patient should be weekly monitored (including Liver Function Tests (LFT) ^f), or more frequently if clinically indicated, until total bilirubin has resolved to baseline or stabilised over 4 weeks
Grade 4 (> 10.0 x ULN)	Discontinue patient from test drug treatment The patient should be weekly monitored (including LFT), or more frequently if clinically indicated, until total bilirubin has resolved to baseline or stabilised over 4 weeks
Isolated AST or ALT elevation	
AST or ALT > 3.0 – 5 x ULN	Omit dose S64315 until resolved to ≤ 3 x ULN, then maintain dose
Grade 3 (> 5.0 - 20.0 x ULN if baseline was normal; >5.0 - 20.0 x baseline if baseline was abnormal)	Omit dose until resolved to ≤ 3 x ULN, then: - If resolved in ≤ 14 days, maintain dose - If resolved in > 14 days, ↓ 1 dose level.
Grade 4 (> 20.0 x ULN if baseline was normal; >20.0 x baseline if baseline was abnormal)	Discontinue patient from test drug treatment

Combined^c elevations of AST or ALT and total bilirubin^e

AST or ALT > 3.0 x ULN combined with total bilirubin > 2.0 x ULN and confirmed Hy's law cases according to FDA guidance

- For patients with normal baseline ALT or AST or total bilirubin value
 - If AST or ALT > 3.0 x ULN combined with total bilirubin > 2.0 x ULN without evidence of cholestasis^d:
 - Permanently discontinue patient from test drug treatment For patients with elevated baseline AST or ALT or total bilirubin value
 - If [AST or ALT > 2.0 x baseline AND > 3.0 x ULN] OR [AST or ALT > 8.0 x ULN], whichever is lower, combined with [total bilirubin > 2.0 x baseline AND > 2.0 x ULN]:
 - Permanently discontinue patient from test drug treatment.
- Repeat LFT^f as soon as possible, perform liver imaging to assess biliary tract or liver disease (if possible), preferably within 48h from awareness of the abnormal results, then with weekly monitoring of LFT^f, or more frequently if clinically indicated, until AST, ALT or bilirubin has resolved to baseline or stabilised over 4 weeks

Investigation (Pancreatic)**Amylase and/or lipase elevation**

Grade 1 (> ULN - 1.5 x ULN)	May maintain dose level
> 1.5 - 2.0 x ULN	May maintain dose level

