Total bilirubin increased (umol/L)	>ULN – 1.5 x ULN if baseline is normal [≤ULN]; 1.0 x baseline – 1.5 x baseline if baseline is abnormal [>ULN]	>1.5 x ULN – 3.0 x ULN if baseline is normal [≤ULN]; >1.5 x baseline – 3.0 x baseline if baseline is abnormal [>ULN]	>3.0 x ULN – 10.0 x ULN if baseline is normal [≤ULN]; >3.0 – 10.0 x baseline if baseline is abnormal [>ULN]	>10.0 x ULN if baseline is normal [≤ULN]; >10.0 x baseline if baseline is abnormal [>ULN]
CPK (IU/l) - high	>ULN – 2.5 x ULN	>2.5 x ULN – 5 x ULN	>5 x ULN – 10 x ULN	> 10 x ULN
Haemoglobin (g/dl) increased	> ULN and increase from baseline]0 ;2] (g/dl)	> ULN and increase from baseline]2 ;4] (g/dl)	> ULN and increase from baseline > 4 (g/dl)	-
Haemoglobin (g/dl) - Anemia	[10;LLN[[8;10[< 8	-
White Blood Cells (g/l) - Low	[3.0;LLN[[2.0;3.0[[1.0;2.0[< 1.0

S 64315

CL1-64315-004 – Statistical Analysis Plan – Final V1.0

Parameter	Grade 1	Grade 2	Grade 3	Grade 4
Neutrophils (g/l) - Low	[1.5;LLN[[1.0;1.5[[0.5;1.0[<0.5
Lymphocytes (g/L) - Low	[0.8;LLN[[0.5;0.8[[0.2;0.5[<0.2
Platelets (g/L) - Low	[75;LLN[[50;75[[25;50[<25
aPTT (sec) - High	>ULN – 1.5 x ULN	>1.5 x ULN – 2.5 x ULN	>2.5 x ULN	-
ALT increased (IU/L)	>ULN – 3.0 x ULN if baseline is normal [\leq ULN]; 1.5 x baseline – 3.0 x baseline if baseline is abnormal [> ULN]	>3.0 x ULN – 5.0 x ULN if baseline is normal [\leq ULN]; >3.0 x baseline – 5.0 x baseline if baseline is abnormal [> ULN]	>5.0 x ULN – 20.0 x ULN if baseline is normal [\leq ULN]; >5.0 x baseline – 20.0 x baseline if baseline is abnormal [> ULN]	>20.0 x ULN if baseline is normal [\leq ULN]; >20.0 x baseline if baseline is abnormal [> ULN]
ALP increased (IU/L)	>ULN – 2.5 x ULN if baseline is normal [\leq ULN]; 2.0 x baseline – 2.5 x baseline if baseline is abnormal [> ULN]	>2.5 x ULN – 5.0 x ULN if baseline is normal [\leq ULN]; 2.5 x baseline – 5.0 x baseline if baseline is abnormal [> ULN]	>5.0 x ULN – 20.0 x ULN if baseline is normal [\leq ULN]; >5.0 x baseline – 20.0 x baseline if baseline is abnormal [> ULN]	>20.0 x ULN if baseline is normal [\leq ULN]; >20.0 x baseline if baseline is abnormal [> ULN]

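### Table (8.12) 1 grades bilirubin against baseline at Grade 2 but against ULN at Grades 3–4, so with an abnormal baseline one value can meet two rows with different dose actions; the AST/ALT rows leave a narrower gap

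*Protocol*

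**What the plan says.** Protocol Table (8.12) 1 is organised by worst CTCAE grade unless otherwise specified, and its footnote a names version 5.0.

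For isolated total bilirubin:
- Grade 2 has two clauses: "Grade 2 (> 1.5 - 3.0 x ULN if baseline was normal, >1.5 - 3.0 x baseline if baseline was abnormal".
- Grade 3 reads "Grade 3 (> 3.0 - 10.0 x ULN" and closes the bracket there, with no baseline clause.
- Grade 4, "Grade 4 (> 10.0 x ULN", has none either.
- After a Grade 2 hold, the dose is kept if the value resolves within 14 days and lowered one level if later. After a Grade 3 hold, it is lowered one level within 14 days and the drug is discontinued if later.

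For isolated AST/ALT the scaling runs the other way:
- The first row, "AST or ALT > 3.0 – 5 x ULN", uses ULN only.
- The next row is "Grade 3 (> 5.0 - 20.0 x ULN if baseline was normal; >5.0 - 20.0 x baseline if baseline was abnormal", and Grade 4 is scaled in the same way.
- Both lower rows hold S64315 until the value is at or below 3 x ULN. They differ only when recovery takes more than 14 days: the first row still keeps the dose, and Grade 3 lowers it one level.

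Abnormal baselines are eligible under protocol section 5.3.2: "AST and ALT < 1.5 x ULN and" the same limit for bilirubin, with total bilirubin up to 3.0 x ULN in Gilbert's syndrome.

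SAP Table (4.2) 4, presented as the CTCAE v5.0 definitions, scales bilirubin Grade 3 to an abnormal baseline: ">3.0 – 10.0 x baseline if baseline is abnormal". It treats Grade 4, and every AST and ALT grade, in the same way. Protocol section 8.2.6 attaches the label Grade 3 to bilirubin above 3 x ULN and to AST or ALT above 5 x ULN, with no baseline clause in either case.

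**The concern.** A dose-modification table should send each value to exactly one row. When adjacent rows use different references, they meet only if baseline equals ULN. Otherwise they overlap, as for bilirubin, or separate, as for AST/ALT. With an overlap, two investigators can follow the protocol to the letter and take different dose actions on the same result. The inconsistent labels add a second difficulty: a value handled as Grade 3 under the protocol table or section 8.2.6 may be tabulated as Grade 2 under the SAP, so dose actions and reported laboratory grades will not line up. Hepatocellular necrosis is among the non-clinical findings in protocol section 2.2.1, and section 8.2.6 calls for close hepatic monitoring.

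**Working it through.** The plan states no figure to reproduce, so the check is interval arithmetic on the tables' own limits. Write the baseline as b x ULN.

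**Inputs.** Row limits: protocol Table (8.12) 1. Eligible b: section 5.3.2, giving 1 < b < 1.5 for an abnormal baseline outside Gilbert's syndrome and b up to 3.0 for bilirubin within it. Comparison limits: SAP Table (4.2) 4 and protocol section 8.2.6.

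**Bilirubin.** For an abnormal baseline, Grade 2 covers (1.5b, 3b] x ULN and Grade 3 covers (3, 10] x ULN. For 1 < b < 1.5 the overlap is (3, 3b], of width 3b − 3 in a Grade 2 band of width 1.5b.

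| b | Grade 2 (x ULN) | Also in Grade 3 (x ULN) | Share of Grade 2 band |
|---|---|---|---|
| 1.0 | 1.5–3.0 | none | 0 |
| 1.2 | 1.8–3.6 | 3.0–3.6 | 0.6/1.8 = 33% |
| 1.4 | 2.1–4.2 | 3.0–4.2 | 1.2/2.1 = 57% |
| 1.49 | 2.235–4.47 | 3.0–4.47 | 1.47/2.235 = 66% |
| 2.0 (Gilbert) | 3.0–6.0 | 3.0–6.0 | all |
| 3.0 (Gilbert) | 4.5–9.0 | 4.5–9.0 | all |

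Example: b = 1.4, value 3.5 x ULN. Relative to baseline it is 3.5/1.4 = 2.5, so Grade 2. Relative to ULN it exceeds 3.0, so Grade 3. Above b = 2, values between 3.0 and 1.5b x ULN are Grade 3 by ULN and below Grade 2 by baseline.

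**AST/ALT.** The first row covers (3, 5] x ULN and Grade 3 starts above 5b x ULN, so (5, 5b] has no row.

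| b | No row (x ULN) |
|---|---|
| 1.0 | none |
| 1.2 | 5.0–6.0 |
| 1.4 | 5.0–7.0 |
| 1.49 | 5.0–7.45 |

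Since b < 1.5, the gap cannot pass 5 x 1.5 = 7.5 x ULN. Example: b = 1.4, value 6 x ULN. It is above the first row and, at 6/1.4 = 4.3 x baseline, below Grade 3.

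**Labels across the documents, b = 1.4.**
- Bilirubin 3.5 x ULN: Grade 2 and Grade 3 in Table (8.12) 1; Grade 3 in section 8.2.6; Grade 2 in the SAP, whose Grade 3 runs from 3 x 1.4 = 4.2 to 10 x 1.4 = 14.0 x ULN.
- Bilirubin between 10 and 14 x ULN: Grade 4 in Table (8.12) 1, Grade 3 in the SAP.
- AST or ALT 6 x ULN: no row in Table (8.12) 1; Grade 3 in section 8.2.6; Grade 2 in the SAP, whose Grade 2 runs from 3 x 1.4 = 4.2 to 5 x 1.4 = 7.0 x ULN.

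On the SAP's definition, bilirubin Grade 3 starts at 3b, where Grade 2 ends, so there is no overlap. That shows only that the two documents differ, not which should give way.

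**The case against.** The best defence is that the notes under Table (8.12) 1 base dose changes on the worst preceding toxicity, so a value meeting two rows goes to the worse one. A site might reasonably do that. But the note chooses among toxicities and does not say what grade a value has. Used as a tie-break, it would cancel the part of the Grade 2 baseline clause above 3.0 x ULN (57% of the band at b = 1.4) and all of it from b = 2. The header's allowance for rows that depart from CTCAE is also fair, but the rows still carry CTCAE grade labels, and the allowance does not remove an overlap between two rows of one table.

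Other parts of the defence stand and limit the point:
- **Gilbert's syndrome.** The widest overlaps arise here, but footnote b gives a separate instruction when a Grade 3 or 4 rise is indirect only and haemolysis is excluded, the asterisked note lets enrolled Gilbert patients continue, and section 6.1.2 bars infusion above 3.0 x ULN. The large-b rows should not carry the argument.
- **AST/ALT.** Section 6.1.2 withholds S64315 above 3 x ULN after LID1 whatever the row, and both neighbouring rows keep the dose if recovery takes 14 days or less.

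Three stronger readings are tempting and are not supported:
- That a bilirubin DLT depends on the scale a site picks. Section 4.1.3.5 grades DLTs by CTCAE v5.0, not by Table (8.12) 1, and the SAP takes DLTs as the investigator reports them.
- That the bilirubin resumption rule contradicts section 6.1.2 ("Total bilirubin level ≤ 1.5 x ULN" outside Gilbert's syndrome). That section sets further conditions before each infusion. Both can be met together, and the stricter one binds.
- That a number of affected patients can be given. The documents report neither how many enter with abnormal values nor how often an on-study value falls in these bands.

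**Conclusion.** The point holds in a limited form. For an eligible patient without Gilbert's syndrome whose baseline bilirubin is above ULN, isolated values from 3.0 to 3b x ULN (never above 4.5 x ULN) meet two rows with different dose actions, and nothing in the protocol settles which applies. For AST/ALT, values from 5 to 5b x ULN have no row, and the open question is only the resumption dose after a recovery of more than 14 days. Separately, three places that use CTCAE grade labels do not agree for abnormal baselines.

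This assumes an isolated elevation and, for bilirubin, one that footnote b does not cover. It does not arise when baseline is normal. Prospective value is also limited: the SAP says escalation was stopped and expansion will not be conducted. What remains is any patient still on treatment, the reading of the safety report, and reuse of the table elsewhere. It is a real inconsistency, worth correcting because the correction is cheap.

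**What to change.** Reconcile the hepatic rows of protocol Table (8.12) 1 with section 8.2.6 and with the CTCAE v5.0 definitions in SAP Table (4.2) 4, so that:
- every isolated bilirubin, AST or ALT value falls in exactly one row, whatever the baseline;
- where the protocol means to act at a threshold other than the CTCAE grade, the row is called a dose-action threshold and not a grade;
- section 8.2.6 uses the same labels as the table.

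The clinical team decides whether ULN or baseline is the reference; this review takes no position. The SAP's grading should not be altered merely to match a dose-action row, because it is presented as CTCAE v5.0. If the protocol is not to be amended again, a sentence in the SAP or study report should say that the reported laboratory grades follow CTCAE v5.0 and can differ from the labels in section 8.12 when baseline is abnormal.

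The cost is wording in two protocol sections or one clarifying sentence. No extra assessments, patients or analyses are needed.

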Creatine kinase (CK) / Creatine phosphokinase (CPK)	Grade ≥ 3 serum CK/CPK Grade 3 isolated electrolyte abnormalities (i.e. those occurring without clinical consequence) not recovered with or without intervention, to Grade < 2 level within 72 hours

TOXICITY	DLT CRITERIA
Electrolyte abnormalities (including magnesium, calcium, phosphorus, etc.) clinically significant	Any Grade 4 electrolyte abnormality
Cardiac disorders	QTcF interval \geq 501 ms or increase of $>$ 60 ms from baseline on at least two separate ECG assessments (1 assessment = triplicate ECG) Asymptomatic, absolute decrease in LVEF of 10% or greater from baseline AND LVEF $<$ 50% Asymptomatic, absolute decrease in LVEF of 20% or greater from baseline Troponin increase $>$ 10xULN or a troponin increase consistent with the diagnosis of a myocardial infarction (Grade 3) Symptomatic congestive heart failure
Skin and subcutaneous tissue disorders	Grade \geq 3 rash
Haematological abnormalities	Grade 4 neutropenia and/or thrombocytopenia persisting for 28 days after the start of azacitidine dosing in a cycle of therapy in the absence of active AML ($<$ 5% blasts) or active MDS or myelofibrosis
Other AEs	Any Grade \geq 3 AE Single event or multiple occurrences of the same event that lead to a dosing delay of $>$ 7 days in a cycle may be considered to be DLT by the Investigators and the Sponsor, even if not Grade \geq 3 Failure to restart test drug administration at the same dose due to drug-related toxicity Failure to restart test drug administration at the same dose within one cycle (i.e. 28 days) of the first missed dose due to delayed recovery from drug-related toxicity Failure to initiate cycle 1 after completing the LID period or failure to receive LID2 after receiving the LID1, due to drug-related toxicity
NCI CTCAE v5.0 will be used for grading	

The following criteria will not be considered as DLT:

- Grade 3 nausea, vomiting, diarrhoea, anorexia or constipation that do not result in hospitalization, tube-feeding or use of TPN
- Grade 3 fatigue, asthenia, fever
- Grade 3 isolated electrolyte abnormalities (i.e. those occurring without clinical consequence) that resolve, with or without intervention, to Grade $<$ 2 level in 72 hours

Patients who meet any of the criteria included in Table (4.1.3.5) 2 at the end of Cycle 1 will not be evaluable for DLT and therefore will be replaced during the dose escalation phase I part of the study, but not in the expansion parts of the study.

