4.1.3.6. DLT management

Study treatments must be delayed for any patient who experienced a DLT. Conditions to resume treatment are described in [section 8.12](#).

All DLT will be reported to I.R.I.S. within 24h via the DLT form in the electronic Case Report Form (eCRF). The eCRF ‘Adverse Event’ page should then be filled in, without waiting for the results of the clinical outcome or of additional investigations. When data of the DLT form are submitted, an e-mail will be immediately and automatically sent to the sponsor.

If the eCRF is unavailable when the investigator is informed of the DLT, he/she should:

- report the DLT on a paper ‘DLT form’
- send the form by fax immediately to I.R.I.S. at the following number: [contact]

As soon as the eCRF becomes available again, the investigator must enter the data in the eCRF.

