8.2.5. Cardiac safety

8.2.5.1. Central ECG recording

In order to monitor the potential of S64315 infusion in combination with azacitidine to delay cardiac repolarisation, serial triplicate 12-lead ECGs (i.e. 3 ECGs within 10 min) will be performed for the measurement of the QT and QTc interval (correction according to Fridericia's formula). 12-lead ECG parameters with at least 3 to 5 QRS complexes for each lead will be evaluated by Core Reading Centre: HR, PR interval, QRS duration, QT interval, RR interval, corrected QT, using Fridericia's formula.

Three print-out ECGs will be produced with at least 6 complexes recorded for each. The ECG recordings will be centrally read by a CRO, specialised in cardiac monitoring. The CRO will provide a 12-lead digital recorder, will train and certify the centres in terms of equipment and will employ a trained independent cardiologist to read the ECGs.

At each time point described in [Table \(8.2\) 2](#), the triplicate 12-lead ECG will be obtained after resting for 10 min prior to the recordings and in supine position. Predose ECG should be collected:

- within 7 days prior to inclusion and results available for inclusion
- after azacitidine injection and before S64315 infusion on CxD2 (day of coadministration)
- with 24h prior to any other S64315 infusion

Detailed instructions on ECG recordings are provided in the ECG manual.

In the event that an ECG abnormality is observed, additional examinations could be performed at the discretion of the investigator (e.g. a blood sample for ionogram (Na, K, Cl) in case of QTc prolongation).

The management of the patient/the study treatment will be based on the local reading of the ECGs; all the ECGs will be sent by the site on a regular basis to the central reading CRO. The final analysis of the QTc values throughout the study will be based on the central reading analysis.

At inclusion visit

The mean QTc will be calculated for each triplicate ECG according to Fridericia's formula. If the mean QTc is > 450 ms in men or > 470 ms in women, then 3 other ECGs (in 10 min) should be repeated 3 h later. The mean QTc will be recalculated. If the abnormality is confirmed, the patient will not be included.

During the study

Triplicate ECGs will be carried-out at the time points defined in [Table \(8.2\) 2](#). The mean QTc will be calculated to detect a possible QTc prolongation. Toxicity grading of QTc interval prolongation is defined by the CTCAE v 5.0 as follows:

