Table (8.2.5.1) 1 - Toxicity grading of QTc interval prolongation is defined by the CTCAE (v 5.0)

Grade	Definition
1	QTc 450 - 480 ms
2	QTc 481 - 500 ms
3	QTc \geq 501 ms on at least two separate ECGs
4	Torsade de pointes or polymorphic ventricular tachycardia or signs/symptoms of serious arrhythmia

In the event of prolongation of the QTc interval according to Fridericia's formula, management of treatments will be performed as explained in the [Table \(8.12\) 1](#).

The recommendations described in the [Table \(8.12\) 1](#) are not intended to supersede the clinical judgment of the investigator and the treating physician, who will determine the appropriate management for the patient. ECG abnormalities considered clinically significant by the investigator will be reported in the eCRF as adverse events.

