Grade 2	Maintain dose level but initiate/intensify appropriate skin toxicity therapy (e.g. antihistamines, topical corticosteroids and low-dose systemic corticosteroids) as per local institutional guidelines and monitor closely Consider skin biopsy for evaluation
Grade 3, despite skin toxicity therapy	Omit dose and reassess the patient weekly until resolved to Grade \leq 1, then: 
 - If resolved in \leq 14 days, \downarrow 1 dose level - If resolved in $>$ 14 days, discontinue patient form test drug treatment Consider referral to dermatologist and manage rash per dermatologist's recommendations Consider skin biopsy for evaluation

Grade 4, despite skin toxicity therapy	Discontinue patient from study treatment Consider referral to dermatologist and manage rash per dermatologist's recommendations Consider skin biopsy for evaluation
Cardiac disorders	
QTcF Prolongation	
QTcF interval \geq 481ms or increase of $>$ 60 ms from baseline on at least two separate ECG	Omit S64315 dose, correct the possible electrolytes abnormalities (e.g. potassium, magnesium, etc.) and perform frequent ECGs* until resolves to Grade \leq 1, then: 
 - If resolved in \leq 14 days, \downarrow 1 dose level. Triplicate ECGs must be monitored on D1 of each cycle throughout the study - If resolved in $>$ 14 days, discontinue patient from test drug treatment *Perform at least weekly ECGs until 2 weeks following resolution of the QTc prolongation
LVEF Decrease	
Asymptomatic, absolute decrease in LVEF of 10% or greater from baseline and LVEF $<$ 50%	Omit dose, obtain consultation with a cardiologist, and repeat cardiac imaging after 4 weeks 
 - If improved to \leq 10% from baseline and \geq 50% within 4 weeks, then \downarrow 1 dose level. Monitor LVEF on D1 of each subsequent cycle for at least 3 cycles; if no recurrence of LVEF decline and if agreed by the cardiologist, the frequency may then be decreased to every other cycle. - If not improved to \leq 10% from baseline and \geq 50% within 4 weeks, then discontinue patient from test drug treatment
Absolute decrease in LVEF of 20% or greater from baseline and LVEF $<$ 40% OR Symptomatic congestive heart failure	Discontinue patient from test drug treatment and obtain consultation with a cardiologist

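### On the protocol's printed QTc grades, a hold triggered only by a QTcF rise above 60 ms already meets its release test, because the release has no baseline-relative term

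*Protocol*

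**What the plan says.** Protocol section 8.12, Table (8.12) 1, gives the QTcF row two alternative triggers for omitting S64315. One is QTcF of at least 481 ms; the other is a rise of more than "60 ms from baseline on at least two separate ECG" recordings. There is a single release test. The site is to "correct the possible electrolytes abnormalities (e.g. potassium, magnesium, etc.) and perform frequent ECGs* until resolves to Grade" 1 or lower. If that takes up to 14 days, S64315 restarts one dose level down, with triplicate ECGs on Day 1 of each later cycle. If it takes longer, the patient discontinues. A footnote adds: "Perform at least weekly ECGs until 2 weeks following resolution of the QTc prolongation".

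The grades are set out in section 8.2.5.1: "Toxicity grading of QTc interval prolongation is defined by the CTCAE v 5.0 as follows". Table (8.2.5.1) 1 then gives Grade 1 as 450 to 480 ms, Grade 2 as 481 to 500 ms and Grade 3 as at least 501 ms on two separate ECGs. None of these bands refers to change from baseline.

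The next row of Table (8.12) 1, for LVEF, uses two recovery conditions. LVEF must return to within "10% from baseline and" to an absolute value of at least 50%.

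**The concern.** The trigger can be relative to baseline, but the release cannot. The rise limb adds something only for patients with a low baseline, since at higher baselines a rise above 60 ms also crosses 481 ms. In those low-baseline patients, the reading that starts the hold already meets the condition that ends it. The row then says both to omit the dose and that the condition for restarting is met.

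Two sites could act differently on the same ECG. One would wait for the rise to fall; the other would reduce the dose and carry on. The 14-day clock has nothing to measure in a rise-only event, and the resolution that ends the weekly ECGs is tied to neither limb.

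No other section supplies a release value. Section 4.1.3.5 lists as a DLT an increase of more than 60 "ms from baseline on at least two separate ECG assessments (1 assessment = triplicate ECG"). Section 4.1.3.6 says "Study treatments must be delayed for any patient who experienced a DLT", but it sends the conditions for resuming back to section 8.12.

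**Working it through.** The documents state no figure to reproduce. The check is whether the trigger and release regions overlap, in whole milliseconds.

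**Inputs**
- Trigger (Table (8.12) 1): QTcF ≥ 481, or QTcF − B > 60, where B is baseline.
- Release (Table (8.12) 1): Grade ≤ 1. By Table (8.2.5.1) 1 this means QTcF ≤ 480.
- Eligible baselines (exclusion criterion 31): up to 450 ms in men and 470 ms in women, so low baselines are admitted.
- Dose levels (Table (4.1.3.3) 1): 25, 50, 100, 200 and 250 mg, with no reduction below 25 mg.

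**Rise-only trigger.** This needs QTcF − B > 60 and QTcF ≤ 480, that is, QTcF from B + 61 to 480. The range is non-empty only if B + 61 ≤ 480, so B ≤ 419. It holds 480 − (B + 61) + 1 = 420 − B values. All are at or below 480 ms, so all meet release.

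**Largest rise permitted at release**, whichever limb began the hold: 480 − B.

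**Release ceiling if a rise of at most 60 ms were also required:** min(480, B + 60).

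| Baseline (ms) | QTcF values meeting trigger and release together | Count | Largest rise at release now (ms) | Ceiling with joint release (ms) |
|---|---|---|---|---|
| 380 | 441–480 | 40 | 100 | 440 |
| 390 | 451–480 | 30 | 90 | 450 |
| 400 | 461–480 | 20 | 80 | 460 |
| 410 | 471–480 | 10 | 70 | 470 |
| 419 | 480 | 1 | 61 | 479 |
| 420 | none | 0 | 60 | 480 |
| 450 | none | 0 | 30 | 480 |

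At baseline 380, nine of the 40 values (441 to 449 ms) lie below Grade 1 altogether. From 420 ms upward a rise above 60 ms gives at least 481 ms, so the absolute limb fires too and the overlap disappears.

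The fourth column also covers a low-baseline patient held for 481 ms or more. At baseline 400, that patient can be released at 480 ms with a rise of 80 ms, which is itself above the trigger.

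**What the restart does to the dose.** One level down is a 20% cut from 250 mg (to 200) and a 50% cut from 200, 100 or 50 mg. From 25 mg no reduction is available.

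**The case against.** The strongest objection concerns the grading. Table (8.12) 1 cites CTCAE v5.0 by footnote, not Table (8.2.5.1) 1. If the full CTCAE text put a confirmed rise above 60 ms higher than Grade 1, release would already require the rise to fall, and the defect would not arise. This stands as a condition on the point. The documents print only the absolute bands and introduce them as the CTCAE v5.0 definition, so that is the reading a site has in hand.

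A second objection is that a sensible reader would give effect to both instructions and hold until the prolongation has actually resolved. For an event judged a DLT, section 4.1.3.6 supports some delay. That is probably what was intended, but it does not say what value ends the delay.

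Third, other rules limit harm. Section 8.12 normally requires discontinuation when a toxicity recurs at the same or worse severity after restart at a lower dose. The row adds weekly and Day 1 ECGs. Section 8.2.5.1 says the recommendations "are not intended to supersede the clinical judgment of the investigator and the treating physician". All of this stands. A reader might infer that patients would be redosed repeatedly without protection; these rules do not support that. The gap left is narrower: a rise that never went away is awkward to call a recurrence, and none of these rules supplies a release value.

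Fourth, an absolute restart threshold with a dose reduction is a defensible choice, since women may enter with QTcF up to 470 ms. But it would then be odd to trigger on the rise at all. The LVEF row is only a partial model, because its trigger joins its two conditions with and, not or.

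**Conclusion.** The point holds on the protocol's printed grading: the QTcF row has a baseline-relative trigger and no baseline-relative release. At whole-millisecond baselines of 419 ms or less, every rise-only hold already meets Grade 1 or lower. The discontinuation branch for slow recovery is not reached while QTcF stays at or below 480 ms, and release is possible with a residual rise of up to 480 minus baseline. The whole-millisecond qualifier matters because triplicate means can be fractional and the printed bands leave 480 to 481 ms ungraded.

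The consequence is small. The documents give neither the share of patients with a baseline of 419 ms or less nor how often such patients rise by more than 60 ms, so no count of affected patients can be stated. A reader might infer that DLT counts or the MTD are distorted. They are not: section 4.1.3.5 has its own QTcF criterion, and SAP section 3.4.6 tabulates QTc values and changes whatever dosing decision was taken. SAP sections 1.3 and 1.3.1 state that escalation was stopped and that neither Arm B nor the expansion will be conducted. The benefit is therefore confined to any patients still on treatment, whom the documents do not show, and to reuse of the table. This is an optional improvement, held with moderate confidence because the full CTCAE text is not in the documents.

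**What to change.** In the QTcF row of Table (8.12) 1, release S64315 only when QTcF is Grade 1 or lower and the rise from baseline is at most 60 ms. Tie the 14-day limit, and the resolution that ends the weekly ECGs, to that joint condition. Trigger and release then cannot overlap at any baseline.

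This is a one-row edit with no new type of assessment. The cost is some longer holds and longer weekly-ECG periods, and possibly a few more discontinuations, in patients with a baseline of 419 ms or less. Nothing changes from 420 ms upward.
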